3.4. Study Duration

The estimated study duration includes a planned 18-month enrollment period followed by a follow-up period of approximately 3.5 years in expected duration (approximately 5 years in total). Patients will be randomized at different times during the enrollment period but will all end the study at the same date (study end date). It is planned that all randomized patients will receive study medication and be followed-up until the study end date. This is an event-driven trial and patients will continue in the trial if the trial runs longer than expected, or will terminate earlier if the trial runs shorter than expected.

The total duration of the trial is based on a median 4-year follow-up period across patients. The first patient randomized would be followed for 4.75 years (the longest individual follow-up duration), and the last patient randomized would be followed for 3.25 year (the shortest individual follow-up duration).

3.5. Study Groups

At Visit 2 (Day 0), eligible study patients will be randomly assigned to the following treatment groups:

- **Group 1:** AMR101 4 g daily (four 1000 mg capsules daily)
- **Group 2:** placebo (four capsules daily)

The four AMR101 or placebo capsules daily will be taken as two capsules in the morning and two capsules in the evening (twice-per-day dosing regimen).

3.6. Number of Patients

This is an event-driven trial: It is expected that a minimum of 1612 primary efficacy endpoint events will be required during the study. A total of approximately 7990 patients will be entered into the study to either receive AMR101 or placebo (approximately 3995 patients per treatment group) in order to observe an estimated 1612 events that make up the primary composite endpoint for efficacy.

3.7. Number of Study Sites

Participants will be enrolled at multiple Research Sites in multiple countries.

3.8. Randomization

On Day 0, eligible patients will be randomized to one of 2 study groups using a computer-generated randomization schema. Randomized treatment assignment to either AMR101 or placebo in a 1:1 ratio will be provided using the internet (IWR).

3.9. Blinding

This is a double-blind study. Patients, investigators, pharmacists and other supporting staff at the Research Sites, personnel and designees of the Sponsor, study administrators and

personnel at the organization(s) and vendors supporting the study will be unaware of the randomization code (i.e., they will not know which study participants are receiving the experimental drug and which are receiving the placebo drug). The study medication AMR101 and placebo capsules will be similar in size and appearance to maintain blinding.

During the double-blind treatment/follow-up period, everyone (patients, investigators, pharmacists and other supporting staff at the Research Sites, personnel and designees of the Sponsor, study administrators and personnel at the organization(s) and vendors managing/supporting the study), with the exception of the laboratory personnel performing the analysis, will be blinded to individual results of the efficacy laboratory measurements (including lipid values). Individual results from the lipid profile may be unblinded in the event of an emergency for a patient.

3.10. Stratification

Participants will be assigned to treatment groups stratified by CV risk category, use of ezetimibe and by geographical region (Westernized, Eastern European, and Asia Pacific countries). There are two CV risk categories:

- CV Risk Category 1: patients with established CVD defined in the inclusion criteria. Patients with diabetes and established CVD are included in this category.
- CV Risk Category 2: patients with diabetes and at least one additional risk factor for CVD, but no established CVD.

Stratification will be recorded in the IWR at the time of enrollment. Approximately 70% of randomized patients will be in the CV Risk Category 1 and approximately 30% of randomized patients will be in the CV Risk Category 2. Enrollment with patients of a CV risk category will be stopped when the planned number of patients in that risk category is reached.

4. STUDY POPULATION

4.1. Inclusion Criteria

Patients meeting the following criteria will be eligible to participate in the study:

1. Fasting TG levels of ≥ 200 mg/dL (2.26 mmol/L) and < 500 mg/dL (5.64 mmol/L).
2. LDL-C > 40 mg/dL (1.04 mmol/L) and ≤ 100 mg/dL (2.60 mmol/L) and on stable therapy with a statin (with or without ezetimibe) for at least 4 weeks prior to the LDL-C/TG baseline qualifying measurements for randomization
 - Stable therapy is defined as the same daily dose of the same statin for at least 28 days before the lipid qualification measurements (TG and LDL-C) and, if applicable, the same daily dose of ezetimibe for at least 28 days before the lipid qualification measurements (TG and LDL-C). Patients who have their statin therapy or use of ezetimibe initiated at Visit 1, or have their statin, statin dose and/or ezetimibe dose changed at Visit 1, will need to go through a stabilization period of at least 28 days since initiation/change and have their qualifying lipid measurements measured (TG and LDL-C) after the washout period (at Visit 1.1).
 - Statins may be administered with or without ezetimibe.

NOTE: If patients qualify at the first qualification visit (Visit 1) for TG and LDL-C, and meet all other inclusion/exclusion criteria, they may be randomized at Visit 2. If patients don't qualify at the first qualifying visit (Visit 1), a second re-qualifying visit (Visit 1.1) is allowed. For some patients, because they need to stabilize medications and/or need to washout medications, the second re-qualifying visit (Visit 1.1) will be needed after the stabilization/washout period.

3. Either having established CVD (in CV Risk Category 1) or at high risk for CVD (in CV Risk Category 2). The CV risk categories are defined as follows:

CV Risk Category 1: defined as men and women ≥ 45 years of age with one or more of the following:

- Documented coronary artery disease (CAD; one or more of the following primary criteria must be satisfied):
 - Documented multivessel CAD ($\geq 50\%$ stenosis in at least two major epicardial coronary arteries – with or without antecedent revascularization)
 - Documented prior MI
 - Hospitalization for high-risk NSTEMI-ACS (with objective evidence of ischemia: ST-segment deviation or biomarker positivity)
- Documented cerebrovascular or carotid disease (one of the following primary criteria must be satisfied):
 - Documented prior ischemic stroke
 - Symptomatic carotid artery disease with $\geq 50\%$ carotid arterial stenosis
 - Asymptomatic carotid artery disease with $\geq 70\%$ carotid arterial stenosis per angiography or duplex ultrasound
 - History of carotid revascularization (catheter-based or surgical)
- Documented peripheral arterial disease (PAD; one or more of the following primary criteria must be satisfied):
 - ABI < 0.9 with symptoms of intermittent claudication
 - History of aorto-iliac or peripheral arterial intervention (catheter-based or surgical)

OR

CV Risk Category 2: defined as patients with:

1. Diabetes mellitus (Type 1 or Type 2) requiring treatment with medication AND
2. Men and women ≥ 50 years of age AND
3. One of the following at Visit 1 (additional risk factor for CVD):
 - Men ≥ 55 years of age or women ≥ 65 years of age;
 - Cigarette smoker or stopped smoking within 3 months before Visit 1;
 - Hypertension (blood pressure ≥ 140 mmHg systolic OR ≥ 90 mmHg diastolic) or on antihypertensive medication;
 - HDL-C ≤ 40 mg/dL for men or ≤ 50 mg/dL for women;

- Hs-CRP >3.00 mg/L (0.3 mg/dL);
- Renal dysfunction: CrCL >30 and <60 mL/min (>0.50 and <1.00 mL/sec);
- Retinopathy, defined as any of the following: non-proliferative retinopathy, preproliferative retinopathy, proliferative retinopathy, maculopathy, advanced diabetic eye disease or a history of photocoagulation;
- Micro- or macroalbuminuria. Microalbuminuria is defined as either a positive micral or other strip test (may be obtained from medical records), an albumin creatinine ratio ≥ 2.5 mg/mmol or an albumin excretion rate on timed collection ≥ 20 mg/min all on at least two successive occasions; macroalbuminuria, defined as albustix or other dipstick evidence of gross proteinuria, an albumin:creatinine ratio ≥ 25 mg/mmol or an albumin excretion rate on timed collection ≥ 200 mg/min all on at least two successive occasions;
- ABI <0.9 without symptoms of intermittent claudication (patients with ABI <0.9 with symptoms of intermittent claudication are counted under CV Risk Category 1).

Note: Patients with diabetes with CVD as defined above are eligible based on the CVD requirements and will be counted under CV Risk Category 1. Only patients with diabetes and no documented CVD as defined above need at least one additional risk factor as listed, and will be counted under CV Risk Category 2.

4. Women may be enrolled if all 3 of the following criteria are met:

- They are not pregnant;
- They are not breastfeeding;
- They do not plan on becoming pregnant during the study.

5. Women of child-bearing potential must have a negative urine pregnancy test before randomization.

Note: Women are not considered to be of childbearing potential if they meet one of the following criteria as documented by the investigator:

- They have had a hysterectomy, tubal ligation or bilateral oophorectomy prior to signing the informed consent form;
- They are post-menopausal, defined as ≥ 1 year since their last menstrual period or have a follicle-stimulating hormone (FSH) level in a menopausal range.

6. Women of childbearing potential must agree to use an acceptable method of avoiding pregnancy from screening to the end of the study, unless their sexual partner(s) is/are surgically sterile or the woman is abstinent.

7. Understanding of the study procedures, willing to adhere to the study schedules, and agreement to participate in the study by giving informed consent prior to screening.

8. Agree to follow a physician recommended diet and to maintain it through the duration of the study.

4.2. Exclusion Criteria

Patients are excluded from participation in the study if any of the following criteria apply:

1. Severe (class IV) heart failure.
2. Any life-threatening disease expected to result in death within the next 2 years (other than CVD).
3. Active severe liver disease (evaluated at Visit 1): cirrhosis, active hepatitis, ALT or AST $>3 \times$ ULN, or biliary obstruction with hyperbilirubinemia (total bilirubin $>2 \times$ ULN).
4. Hemoglobin A_{1c} $>10.0\%$ (or 86 mmol/mol IFCC units) at screening (Visit 1). If patients fail this criterion (HbA_{1c} $>10.0\%$ or 86 mmol/mol IFCC units) at Visit 1, they may have their antidiabetic therapy optimized and be retested at Visit 1.1.
5. Poorly controlled hypertension: blood pressure ≥ 200 systolic mmHg OR ≥ 100 mmHg diastolic (despite antihypertensive therapy).
6. Planned coronary intervention (such as stent placement or heart bypass) or any non-cardiac major surgical procedure. Patients can be (re)evaluated for participation in the trial (starting with Visit 1.1) after their recovery from the intervention/surgery.
7. Known familial lipoprotein lipase deficiency (Fredrickson Type I), apolipoprotein C-II deficiency, or familial dysbetalipoproteinemia (Fredrickson Type III)].
8. Participation in another clinical trial involving an investigational agent within 90 days prior to screening (Visit 1). Patients cannot participate in any other investigational medication or medical device trial while participating in this study (participation in a registry or observational study without an additional therapeutic intervention is allowed).
9. Intolerance or hypersensitivity to statin therapy.
10. Known hypersensitivity to any ingredients of the study product or placebo (refer to Table 3); known hypersensitivity to fish and or shellfish.
11. History of acute or chronic pancreatitis.
12. Malabsorption syndrome and/or chronic diarrhea (Note: patients who have undergone gastric/intestinal bypass surgery are considered to have malabsorption, hence are excluded; patients who have undergone gastric banding are allowed to enter the trial).
13. Non-study drug related, non-statin, lipid-altering medications, supplements or foods:
 - Patients are excluded if they used niacin >200 mg/day or fibrates during the screening period (after Visit 1) and/or plan to use during the study; patients who are taking niacin >200 mg/day or fibrates during the last 28 days before Visit 1 need to go through washout of at least 28 days after their last use and have their qualifying lipids measured (TG and LDL-C) after the washout period (Visit 1.1);
 - Patients are excluded if they take any omega-3 fatty acid medications (prescription medicines containing EPA and/or DHA) during the screening period (after Visit 1) and/or plan to use during the treatment/follow-up period of the study. To be eligible for participation in the study, patients who are taking omega-3 fatty acid medications

during the last 28 days before Visit 1 (except patients in The Netherlands), need to go through a washout period of at least 28 days after their last use and have their qualifying lipids measured (TG and LDL-C) after the washout period (at Visit 1.1);

- For patients in The Netherlands only: patients being treated with omega-3 fatty acid medications containing EPA and/or DHA are excluded; no washout is allowed.
- Patients are excluded if they use dietary supplements containing omega-3 fatty acids (e.g., flaxseed, fish, krill, or algal oils) during the screening period (after Visit 1) and/or plan to use during the treatment/follow-up period of the study. To be eligible for participation in the study, patients who are taking >300 mg/day omega-3 fatty acids (combined amount of EPA and DHA) within 28 days before Visit 1 (except patients in The Netherlands), need to go through a washout period of at least 28 days since their last use and have their qualifying lipid measurements measured (TG and LDL-C) after the washout period (at Visit 1.1);
 - For patients in The Netherlands only: patients being treated with dietary supplements containing omega-3 fatty acids of >300 mg/day EPA and/or DHA are excluded; no washout is allowed.
- Patients are excluded if they use bile acid sequestrants during the screening period (after Visit 1) and/or plan to use during the treatment/follow-up period of the study. To be eligible for participation in the study, patients who are taking bile acid sequestrants within 7 days before Visit 1, need to go through a washout period of at least 7 days since their last use and have their qualifying lipid measurements measured (TG and LDL-C) after the washout period (at Visit 1.1);

14. Other medications (not indicated for lipid alteration):

- Treatment with tamoxifen, estrogens, progestins, thyroid hormone therapy, systemic corticosteroids (local, topical, inhalation, or nasal corticosteroids are allowed), HIV-protease inhibitors that have not been stable for ≥ 28 days prior to the qualifying lipid measurements (TG and LDL-C) during screening. To be eligible for participation in the study, patients who are not taking a stable dose of these medications within 28 days before Visit 1, need to go through a stabilization period of at least 28 days since their last dose change and have their qualifying lipid measurements measured (TG and LDL-C) after the washout period (at Visit 1.1).
- Patients are excluded if they use cyclophosphamide or systemic retinoids during the screening period (after Visit 1) and/or plan to use during the treatment/follow-up period of the study. To be eligible for participation in the study, patients who are taking these medications within 28 days before Visit 1, need to go through a washout period of at least 28 days since their last use and have their qualifying lipid measurements measured (TG and LDL-C) after the washout period (at Visit 1.1).

15. Known to have AIDS (patients who are HIV positive without AIDS are allowed).

16. Requirement for peritoneal dialysis or hemodialysis for renal insufficiency or if creatinine clearance (CrCL) <30 mL/min (0.50 mL/sec).

17. Unexplained creatine kinase concentration $>5 \times$ ULN or creatine kinase elevation due to known muscle disease (e.g., polymyositis, mitochondrial dysfunction) at Visit 1.
18. Any condition or therapy which, in the opinion of the investigator, might pose a risk to the patient or make participation in the study not in the patient's best interest.
19. Drug or alcohol abuse within the past 6 months, and unable/unwilling to abstain from drug abuse and excessive alcohol consumption during the study or drinking 5 units or more for men or 4 units or more for women in any one hour (episodic excessive drinking or binge drinking). Excessive alcohol consumption is on average >2 units of alcohol per day. A unit of alcohol is defined as a 12-ounce (350 mL) beer, 5-ounce (150 mL) wine, or 1.5-ounce (45 mL) of 80-proof alcohol for drinks.
20. Mental/psychological impairment or any other reason to expect patient difficulty in complying with the requirements of the study or understanding the goal and potential risks of participating in the study (evaluated at Visit 1).

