9.2.2. Secondary Efficacy Endpoints

The key secondary efficacy endpoint is:

- The composite of death from CV causes, nonfatal MI, coronary revascularization, unstable angina determined to be caused by myocardial ischemia by invasive/non-invasive testing and requiring emergent hospitalization, nonfatal stroke, or peripheral CVD requiring intervention, angioplasty, bypass surgery, or aneurysm repair.

Other secondary efficacy endpoints are as follows (to be tested in said order):

- The composite of total mortality, nonfatal MI, or nonfatal stroke;
- The composite of death from CV causes, nonfatal MI, coronary revascularization, unstable angina determined to be caused by myocardial ischemia by invasive/non-invasive testing and requiring emergent hospitalization, peripheral CVD requiring intervention, or cardiac arrhythmia requiring hospitalization;
- The composite of death from CV causes, nonfatal MI, coronary revascularization, or unstable angina determined to be caused by myocardial ischemia by invasive/non-invasive testing and requiring emergent hospitalization;
- The composite of death from CV causes or nonfatal MI;
- Total mortality;
- Fatal and nonfatal MI (including silent MI);
- Coronary Revascularization;
- Hospitalization for unstable angina determined to be caused by myocardial ischemia by invasive/non-invasive testing ;
- Fatal and nonfatal stroke.

For the secondary endpoints that count a single event, the first occurrence of this type of event will be counted in each patient. For secondary endpoints that are composites of two or more types of events, the first occurrence of any of the event types included in the composite will be counted in each patient.

9.2.3. Tertiary Efficacy Endpoints:

- The second, third, fourth, and fifth major CV event of the primary composite endpoint. The type of (nonfatal) events may occur in any order.
- Primary endpoint in subset of patients with diabetes mellitus;
- Primary endpoint in subset of patients with metabolic syndrome;
- New CHF, new CHF leading to hospitalization, transient ischemic attack, amputation for CVD and carotid revascularization;
- Elective coronary revascularization and emergent coronary revascularization;
- New onset diabetes;
- Fasting TG, TC, LDL-C, HDL-C, non-HDL-C, VLDL-C, apo B, hs-CRP, and hsTnT: effect of baseline and on-treatment change of biomarkers on primary and key secondary endpoints;

- CV mortality;
- Cardiac Arrhythmias requiring hospitalization;
- Cardiac Arrest;

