 - c. Death witnessed and attributed to an identified arrhythmia (e.g., captured on an electrocardiographic (ECG) recording, witnessed on a monitor, or unwitnessed but found on implantable cardioverter-defibrillator review)
 - d. Death after unsuccessful resuscitation from cardiac arrest
 - e. Death after successful resuscitation from cardiac arrest and without identification of a non-cardiac etiology
 - f. Unwitnessed death without other cause of death (information regarding the patient's clinical status preceding death should be provided, if available)

General Considerations

A subject seen alive and clinically stable 12-24 hours prior to being found dead without any evidence or information of a specific cause of death should be classified as "sudden cardiac death."

- Deaths for which there is no information beyond “Patient found dead at home” may be classified as “death due to other cardiovascular causes” or in some trials, “undetermined cause of death.” Please see Definition of Undetermined Cause of Death, for full details.
3. **Death due to Congestive Heart Failure** refers to a death in association with clinically worsening symptoms and/or signs of heart failure (see Definition of Heart Failure Event). Deaths due to heart failure can have various etiologies, including single or recurrent myocardial infarctions, ischemic or non-ischemic cardiomyopathy, hypertension, or valvular disease.
 4. **Death due to Stroke** refers to death after a stroke that is either a direct consequence of the stroke or a complication of the stroke. Acute stroke should be verified to the extent possible by the diagnostic criteria outlined for stroke (see Definition of Transient Ischemic Attack and Stroke).
 5. **Death due to Cardiovascular Procedures** refers to death caused by the immediate complications of a cardiac procedure.
 6. **Death due to Cardiovascular Hemorrhage** refers to death related to hemorrhage such as a non-stroke intracranial hemorrhage (see Definition of Transient Ischemic Attack and Stroke), non-procedural or non-traumatic vascular rupture (e.g., aortic aneurysm), or hemorrhage causing cardiac tamponade.
 7. **Death due to Other Cardiovascular Causes** refers to a CV death not included in the above categories (e.g., pulmonary embolism or peripheral arterial disease).

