23.10. Definition of Peripheral Vascular Intervention

1. Peripheral Vascular Intervention (PVI): Peripheral vascular intervention is a catheter-based or open surgical procedure designed to improve peripheral arterial or venous blood flow or otherwise modify or revise vascular conduits. Procedures may include, but are not limited to, balloon angioplasty, stent placement, thrombectomy, embolectomy, atherectomy, dissection repair, aneurysm exclusion, treatment of dialysis conduits, placement of various devices, intravascular thrombolysis or other pharmacotherapies, and open surgical bypass or revision.

In general, the intention to perform *percutaneous* peripheral vascular intervention is denoted by the insertion of a guide wire into a peripheral artery or vein.

The target vessel(s) and the type of revascularization procedure (e.g., surgical bypass, thrombectomy, endarterectomy, percutaneous angioplasty, stent placement, thromboembolectomy, and thrombolysis) should be specified and recorded. For the sake of simplicity, this definition applies to the extracranial carotid artery and other non-cardiac arteries and veins and excludes the intracranial vessels and lymphatics.

2. **Procedural Success:** In the case of percutaneous intervention for obstructive lesions, procedural success is defined as the achievement of a satisfactory final residual diameter stenosis by angiography at the end of the procedure (and without flow limiting dissection or hemodynamically significant translesional pressure gradient). The specific parameter for final percent residual stenosis is typically between < 30% and < 50%; selection of the appropriate percentage may vary depending upon the specific intervention applied, the vascular territory, and anticipated or desired therapeutic response. Procedural success also implies absence of in-hospital major adverse events (e.g., death, stroke, myocardial infarction, acute onset of limb ischemia, need for urgent/emergent vascular surgery, and other procedure-specific major adverse events). The balloon inflation, stent placement, or other therapeutic intervention may be preceded by use of adjunctive devices (e.g., percutaneous mechanical thrombectomy, directional or rotational atherectomy, laser, and chronic total occlusion crossing device), as predefined in the protocol.
3. **Procedural Status: Non-Elective and Elective:**

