 - a. **Non-Elective:** Non-elective procedures include emergent and urgent procedures. A non-elective procedure is a procedure that is performed without delay, because there is clinical consensus that the procedure should occur imminently. Non-elective procedures imply a degree of instability of the patient, urgency of the medical condition, or instability of the threatening lesion.
 - **Emergent:** A procedure that is performed immediately because of the acute nature of the medical condition (e.g., acute limb ischemia, acute aortic dissection), and the increased morbidity or mortality associated with a temporal delay in treatment.

- **Urgent:** An urgent procedure is one that is not emergent but required to be performed on a timely basis (≤ 24 hrs) (e.g., a patient who has been stabilized following initial treatment of acute limb ischemia, and there is clinical consensus that a definitive procedure should occur within the next 24 hours).
- b. Elective:** An elective procedure is one that is scheduled and is performed on a patient with stable disease, or in whom there is no urgency and/or increased morbidity or mortality associated with a planned procedure.
1. **Target Lesion:** A target lesion is any lesion treated or attempted to be treated during the trial procedure with the index device. The target lesion is the treated segment starting 5 mm proximal and ending 5 mm distal to the index device (stent, in most cases).
 2. **Target Vessel:** A target vessel is any vessel (e.g., non-cardiac or non-cerebrovascular vessel) that contains the target lesion treated with the study device. The target vessel includes the target lesion as well as the entire vessel upstream and downstream to the target lesion, including side branches (native vessel).
 3. **Non-Target Lesion:** A non-target lesion is one for which revascularization is not attempted or one in which revascularization is performed using a non-study device.
 4. **Non-Target Vessel:** A non-target vessel is one for which revascularization is not attempted or one in which revascularization is performed using a non-study device.
 5. **Target Vessel, Non-Target Lesion:** Any lesion or revascularization of a lesion in the target vessel other than the target lesion.

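### Exclusion 6 does not name planned catheter-based peripheral or carotid procedures, so a procedure booked before randomization can count as a key secondary event; the effect is a small dilution

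*Combined protocol and SAP*

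**What the plan says.** Exclusion 6 is worded the same in the synopsis and section 4.2, in both the 2011 protocol and Amendment 1. It has two limbs: "Planned coronary intervention (such as stent placement or heart bypass) or any non-cardiac major surgical procedure". It then allows re-evaluation after recovery.

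Section 4.1 (Amendment 1) admits to CV Risk Category 1 patients with a low ankle-brachial index and claudication, and patients with symptomatic or asymptomatic carotid stenosis above set thresholds. The same list treats catheter and surgical routes as alternatives, as in "History of carotid revascularization (catheter-based or surgical".

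On the endpoint side:

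- Section 9.2.2 makes "peripheral CVD requiring intervention, angioplasty, bypass surgery, or aneurysm repair" a component of the key secondary endpoint. Peripheral CVD requiring intervention is also in the second of the other secondary composites, which are tested in order.
- Section 9.2.3 lists carotid revascularization as a tertiary endpoint.
- Appendix B, 23.10, includes catheter-based procedures, states that "this definition applies to the extracranial carotid artery and other non-cardiac arteries and veins", and recognises an elective category: "An elective procedure is one that is scheduled and is performed on a patient with stable disease".
- The one exception for planned procedures in Appendix B is in 23.6, and it concerns only hospitalization for unstable angina.

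**The concern.** Exclusion 6 stops a coronary procedure already booked at entry from later being counted as an outcome. The key secondary endpoint adds a peripheral component, but the exclusion was not widened to match. Read literally, a patient with an iliac or carotid stent on the calendar is eligible, and the stent is then available to be counted, although the decision to do it came before the first dose.

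Such events occur in both arms at the same expected rate, so they add to both event counts and pull the hazard ratio toward 1. The key secondary endpoint opens the sequential procedure in section 12.2.4.3, so any power lost there is passed on to every endpoint below it. The trial stops on primary events, so these extra key secondary events bring no additional follow-up to compensate.

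**Working it through.** **Does the text admit and count these procedures?**

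1. Coronary limb: a peripheral or carotid stent is not coronary.
2. Surgical limb: planned open bypass, endarterectomy or open aneurysm repair is non-cardiac major surgery and is already excluded. A catheter procedure is not clearly surgery, because section 4.1 separates the two routes. The term for major surgery is not defined, so sites may differ.
3. Other criteria: the nearest is exclusion 18, "Any condition or therapy which, in the opinion of the investigator, might pose a risk to the patient". It turns on the investigator's opinion and does not name planned procedures.
4. Endpoint: an elective, scheduled peripheral procedure fits 23.10, and nothing in 9.2 or Appendix B removes one scheduled before randomization.

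**The plan's own figure.** With a hazard ratio of 0.85, two-sided alpha 0.0476 and 90% power (section 12.3), the Schoenfeld formula gives 4 × (1.981 + 1.282)² / (ln 0.85)² = 1612 events, as stated. No event count or power is given for the key secondary endpoint.

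**Inputs for the dilution**

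- From the plan: 7990 patients, 1:1 allocation, hazard ratio 0.85 (the 15% reduction), and alpha 0.05 two-sided for secondary endpoints.
- Assumed: G = 1700 genuine key secondary events. It cannot be below 1612 when that many patients have primary events, because every primary event is also a key secondary event.
- Assumed: a share f of 0.25% to 1% of patients has such a procedure scheduled, and all of these count.

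**Formulas.** Genuine events split as 1700 × 0.85/1.85 = 781.1 on AMR101 and 1700/1.85 = 918.9 on placebo. With k = 7990 × f planned events shared equally:

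- observed HR = (781.1 + k/2) / (918.9 + k/2)
- power = Φ( √(1700 + k)/2 × |ln HR| − 1.96 )

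| f | k | Observed HR | Power |
|---|---|---|---|
| 0 | 0 | 0.850 | 91.8% |
| 0.25% | 20 | 791.1/928.9 = 0.8516 | 91.5% |
| 0.5% | 40 | 801.1/938.9 = 0.8532 | 91.2% |
| 1% | 80 | 821.0/958.9 = 0.8562 | 90.6% |

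**A check on the simplification.** The table adds planned events without removing any genuine ones. A patient whose first event is the planned procedure can no longer contribute a later first event. If genuine events fall by the same 1%, to 1683, the last row becomes (773.3 + 39.95)/(909.7 + 39.95) = 0.856, with power 90.3%. The picture does not change.

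**The case against.** The strongest reply is that the effect is negligible. On the assumptions above, the key secondary endpoint loses 0.3 to 1.2 points of power, and neither the share of patients with peripheral or carotid disease nor a rate of booked procedures is documented. That stands, and it limits this point to a cheap improvement.

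Other parts of the reply also stand:

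- **Unseen text.** Section 9.1 refers further detail on event assessment to the CEC charter, which was not available and may already discount pre-scheduled procedures. Only the title page of Amendment 2 (v3.0, July 2016) was available, so this point concerns the Amendment 1 text.
- **Investigator judgment.** Exclusion 18 leaves room to keep some of these patients out, and a site may read major surgery broadly enough to cover endovascular work.
- **Carotid status is mixed.** 23.10 covers the extracranial carotid, but 23.11 lists carotid apart from peripheral, and section 9.2.3 gives it its own endpoint. Putting every carotid procedure in the key secondary endpoint is therefore the less favourable reading.

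The reply does not remove the gap itself. A charter governs adjudication, not eligibility, and as written the criterion does not name these procedures.

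**Conclusion.** The gap is real on the Amendment 1 text, and its effect is small. Under the stated assumptions the key secondary hazard ratio moves from 0.85 to about 0.852 to 0.856 and power from 91.8% to between 91.5% and 90.6%. The direction is toward no effect.

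A reader might infer more, and the documents do not support it:

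- **That the primary endpoint is contaminated.** Peripheral, carotid and valve procedures are not primary components. Planned non-coronary cardiac procedures are also not named in exclusion 6, but only their complications could count. For example, CV death under 23.1 includes a category that "refers to death caused by the immediate complications of a cardiac procedure". Such complications are not fixed before dosing, and the documents give nothing from which to size them. A bypass graft planned alongside valve surgery is already excluded as a planned coronary intervention.
- **That the peripheral component is badly distorted.** With an assumed 100 to 150 genuine events, its hazard ratio alone would read 0.87 to 0.91. That component is not a listed endpoint, and the component breakdown in section 12.2.4.2 is for the primary composite.
- **That the result could be falsely positive.** Randomization balances these patients on average, so the effect is dilution only.

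**What to change.** Reword exclusion 6 in section 4.2 and the synopsis to: *Planned coronary, other cardiac, carotid or peripheral arterial intervention (catheter-based or surgical), or any planned non-cardiac major surgical procedure.* Keep the existing provision for re-evaluation after recovery.

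For patients already randomized, leave the endpoint definition as it is. While the trial is blinded, record whether each peripheral or carotid procedure had been scheduled before randomization. Then report a sensitivity analysis of the key secondary endpoint that does not count those procedures. If the CEC charter already discounts them, this second step is not needed.

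The cost is one eligibility sentence, one CRF item and one sensitivity analysis. A few patients would be deferred until after their procedure, which exclusion 6 already provides for in coronary cases.
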